#### **8.1.2. Growth**

To adjust study medication for weight gain, weight will be recorded at multiple study visits. To assess renal function, length will be recorded at multiple study visits for use in calculating creatinine clearance.

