**Usual Social & Functional Activities – Young Children:** Activities that are age and culturally appropriate (e.g., social interactions, play activities, learning tasks, etc.).

CLINICAL				
PARAMETER	GRADE 1 MILD	GRADE 2 MODERATE	GRADE 3 SEVERE	GRADE 4 POTENTIALLY LIFE-THREATENING
Pain (indicate body site) DO NOT use for pain due to injection (See Injection Site Reactions: Injection site pain) See also Headache, Arthralgia, and Myalgia	Pain causing no or minimal interference with usual social & functional activities	Pain causing greater than minimal interference with usual social & functional activities	Pain causing inability to perform usual social & functional activities	Disabling pain causing inability to perform basic self-care functions OR Hospitalization (other than emergency room visit) indicated
Unintentional weight loss	NA	5 – 9% loss in body weight from baseline	10 – 19% loss in body weight from baseline	≥ 20% loss in body weight from baseline OR Aggressive intervention indicated [e.g., tube feeding or total parenteral nutrition (TPN)]
INFECTION				
Infection (any other than HIV infection)	Localized, no systemic antimicrobial treatment indicated AND Symptoms causing no or minimal interference with usual social & functional activities	Systemic antimicrobial treatment indicated OR Symptoms causing greater than minimal interference with usual social & functional activities	Systemic antimicrobial treatment indicated AND Symptoms causing inability to perform usual social & functional activities OR Operative intervention (other than simple incision and drainage) indicated	Life-threatening consequences (e.g., septic shock)
INJECTION SITE REACTIONS				
Injection site pain (pain without touching) Or Tenderness (pain when area is touched)	Pain/tenderness causing no or minimal limitation of use of limb	Pain/tenderness limiting use of limb OR Pain/tenderness causing greater than minimal interference with usual social & functional activities	Pain/tenderness causing inability to perform usual social & functional activities	Pain/tenderness causing inability to perform basic self-care function OR Hospitalization (other than emergency room visit) indicated for management of pain/tenderness
Injection site reaction (localized)				

**Basic Self-care Functions – Adult:** Activities such as bathing, dressing, toileting, transfer/movement, continence, and feeding.

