4.1 General Study Design and Plan

[figure not shown]
(ICH E3;9)

The current study evaluates whether six weeks of antiviral therapy can stabilize hearing deterioration in older infants, toddlers, and young children who have developed CMV-associated hearing loss. This study is a Phase II, international, multi-center, double-blind, placebo-controlled evaluation of six weeks of valganciclovir treatment for children (up to 4 years of age) with virologically-confirmed congenital CMV infection and hearing loss.

Patients meeting inclusion/exclusion criteria will be offered enrollment into the trial. Randomization on the study occurs when the diagnosis of congenital CMV infection is confirmed, and the subject is then assigned to receive either 6 weeks of oral valganciclovir or 6 weeks of placebo. Study subjects will be stratified according to age at randomization (1 through 11 months, 12 through 23 months, 24 through 35 months, and ≥ 36 months) and CMV involvements (symptomatic and asymptomatic at birth) as a marker of disease severity. An independent Data and Safety Monitoring Board (DSMB) will oversee the conduct of the trial. During the course of their oversight, they may request to have access to unblinded data.

The target sample size is 54 subjects (27 in each arm). Up to 20% over-enrollment will be allowed to replace subjects who drop-out or who have inadequate audiology assessments. The primary endpoint will be change in total ear hearing assessments (improved + no change versus other) between baseline and 6 months. Secondary and tertiary endpoints will be assessments of other measures of hearing outcomes; detection of viruria, viremia, and CMV in saliva by PCR six weeks and six months after trial entry; the quantitative log reduction in viruria, viremia, and CMV viral load in saliva detected after six weeks of therapy; correlation of change in viral load with change in total ear and best ear hearing at six months; incidences of unanticipated medically attended visits and adverse events which lead to permanent discontinuation of valganciclovir therapy or have an unresolved outcome; and assessments of blood concentration of ganciclovir after administration of valganciclovir. Stopping rules will be employed in order to limit exposure of study subjects to a potentially unacceptable treatment.

Figure 1: Schematic of Study Design

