4.5 Study Variables

(ICH E3; 9.5.1. ICH E9; 2.2.2)

The following table summarizes the visit, visit windows and the information to be collected and evaluations to be done at each visit.

| | Enrollment (Window: Day -90 to Day -1) | Randomization (Window: Day -30 to Day 1) | Study Day | | | | | Study Month | |
|---|---|---|------------------------|------------------|------------------|------------------|------------------|-----------------|-----------------|
| | | | 1 (day -3 to day 1) | 14 (± 2 days) | 28 (± 2 days) | 42 (± 2 days) | 70 (± 4 days) | 4 (± 7 days) | 6 (± 7 days) |
| Following study enrollment, testing of Guthrie card for CMV DNA by PCR (if congenital CMV infection has not already been documented during first month of life) | X | | | | | | | | |
| Confirmation of congenital CMV infection by documentation during first month of life or by PCR-positive Guthrie card | | X | | | | | | | |
| Baseline demographics ^a | | X | | | | | | | |
| Hematology Safety Labs ^b | | | X | X | X | X | X | | |
| Chemistry Safety Labs ^c | | | X | X | X | X | X | | |
| Weight and Length | | | X | X | X | | | | |
| Adverse Event Assessment | | | X | X | X | X | X | | |
| Concurrent Medications | | | X | X | X | X | X | | |
| Updated results of any etiological investigations for SNHL | | | X | X | X | X | X | X | X |
| Hearing Assessment | | X ^d Day -90 to Day -1 | | | | | | | X 14-30 days |
| Virology Specimens for CMV Viral Load ^e | | | X | X | X | X | X | X | X |
| Ganciclovir Population Pharmacokinetics ^f | | | | X | X | X | | | |

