9.6 Other Safety Measures

Growth parameters (weight and length) will be captured serially. Fisher's exact test will be used to compare proportions and Wilcoxon rank sum test will be used to compare continuous safety parameters between two groups at each visit. Growth parameters will be presented graphically to monitor trends and compared at each time point for possible differences. The summary statistics will be produced in accordance with section 7.

10 Pharmacokinetics

If the final number of usable PK specimens warrants, a population PK model may be applied to the dataset. The population PK modeling will be conducted using ADAPT 5 version 049.exe (Biomedical Simulations Resource, Los Angeles, CA), installed on a Dell Latitude E6410 laptop running Windows 7.0, 64 bit operating system (Intel Visual Fortran Compiler Professional Edition 11.1.070 Update 8 for Windows and Intel Math Kernel Library 10.2 Update 7 for Windows). For the analysis, all time values will be truncated. Instead of entering 6 weeks of dosing information, the timeline will be reduced to generally within 3-5 days depending upon the number of available concentration-time points for each subject. Thus, all samples will be still at steady-state. Population PK analysis will be conducted via a nonlinear mixed-effect model approach using ADAPT 5. The Maximum Likelihood Estimation Maximization (MLEM) algorithm will be used for all analyses. The PK base model will be identified previously as a one-compartment model with first-order input and

elimination. All inter-individual error terms in the PK parameters will be assumed to have a log-normal distribution. One error variance model will be used:

$$\text{var}\{e(t)\} = (\sigma_{inter} + \sigma_{slope}y(t))^2$$

where the proportional error model is σ_{slope} and the additive error model is σ_{inter} . This is the most common error variance model used in ADAPT.

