| Table 18b: Weight (kg) at the Time of Dosing of Valganciclovir or Placebo | 18b | At least one dose of study drug | Dose | Day 1, 14 28 | Therapy Group, Visit | N, Mean, SD, Median, Min, Max | General linear mixed model with random intercept was fitted for each parameter. Each model contains therapy, time and therapy by time interaction. |
| Table 18c: Length (cm) at the Time of Dosing of Valganciclovir or Placebo | 18c | At least one dose of study drug | Weight | Day 1, 14 28 | Therapy Group, Visit | N, Mean, SD, Median, Min, Max | General linear mixed model with random intercept was fitted for each parameter. Each model contains therapy, time and therapy by time interaction. |
| Table 19a: Dosing Administration by Treatment Group and Visit | 19 | At least one dose of study drug | Length | Day 1, 14 28 | Therapy Group, Visit | n, % | Fisher's exact |
| Table 19b: Reasons for Adjusted or Held Dose and Significant Changes in Laboratory Parameters | 19a | At least one dose of study drug | Dose | Day 1, 14 28 | Therapy Group, Visit | n, % | Fisher's exact |
| Table 20: PK Specimen Results: GCV concentration in the Active Group | 19b | At least one dose of study drug | Dose | Day 1, 14 28 | NA | N, Mean, SD, Median, Min, Max | NA |
| Table 21a: Quality of Hearing Assessment Left and Right (Total Ear) | 20 | At least one dose of study drug | GCV concentration | Day 14, 28, 42 | NA | n, % | NA |
| Table 21b: Hearing Assessment Left and Right (Total Ear) | 21a | At least one dose of study drug | Quality of Total Ear Assessment | Baseline and Month 6 | Therapy Group, Visit | n, % | NA |
| Table 21c: Change in Total Ear Hearing at Month 6 Relative to Baseline | 21b | At least one dose of study drug | Hearing Assessment Total Ear | Baseline and Month 6 | Therapy Group, Visit | n, % | NA |

| | | | | | | | |
|---|-----|---------------------------------|--|----------------------|--|-----------------------------------|---|
| Table 21d: Results of Modeling Treatment Effect on Total Ear For Each Outcome | 21c | At least one dose of study drug | Change in Total Ear Hearing Assessment | Baseline and Month 6 | Therapy Group | n, %, p-value | Generalized linear model for binary outcome using GEE was fitted for each parameter. Each model contains therapy, time and therapy by time interaction. |
| Table 21e: Subgroup Analysis (Total Ears) | 21d | At least one dose of study drug | Change in Total Ear Hearing Assessment | Baseline and Month 6 | Therapy Group | n, % | NA |

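### SAP 9.6 states a by-visit Wilcoxon test on recorded weight and length as its growth comparison; it should name the change from Day 1 to Day 28 instead, as Tables 18b/18c already nearly do.

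*SAP*

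**What the plan says.** SAP 9.6 (Other Safety Measures) covers weight and length. For continuous measures it states that the "Wilcoxon rank sum test will be used to compare continuous safety parameters between two groups at each visit", and it adds: "Growth parameters will be presented graphically to monitor trends and compared at each time point for possible differences". It defines no change from Day 1, no adjustment for the Day 1 value or age, and no age-standardised score.

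The list of tables in SAP Section 17 goes further. It includes "Table 18b: Weight (kg) at the Time of Dosing of Valganciclovir or Placebo" and a matching Table 18c for length, both on Days 1, 14 and 28 by therapy group. The formal analysis for both is a mixed model with a random intercept: "Each model contains therapy, time and therapy by time interaction". Section 9.6 does not mention these tables.

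Three other places set the context:

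- SAP 4.1: "Study subjects will be stratified according to age at randomization", in four bands (1-11, 12-23, 24-35 and 36 or more months), crossed with symptomatic or asymptomatic status at birth.
- SAP 4.5: weight and length are scheduled on Days 1, 14 and 28 only.
- Protocol 8.1.2: "To adjust study medication for weight gain, weight will be recorded at multiple study visits"; length is recorded for creatinine clearance.

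**The concern.** A rank test on Day 28 weight asks whether children in one arm are heavier than children in the other. With ages from 1 month to nearly 4 years, the answer is almost entirely about age. A treatment effect on growth over 28 days is a fraction of a kilogram, against a spread between children of several kilograms. The test also ignores the age strata. Stratified allocation makes the arms more alike in age than the test's reference distribution assumes, so the test becomes conservative as well as insensitive.

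What is at stake is how a null result is read. A report following the text of 9.6 would almost always find no difference in growth, whatever the truth, and that could be taken as reassurance. The error runs one way: the test can miss a signal but does not manufacture one. Growth is of some interest in either direction, because Protocol 2.1.2.1 reports greater weight gain at six weeks with intravenous ganciclovir than with no treatment.

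**Working it through.** **No plan figure to reproduce.** The documents give no effect size, standard deviation (SD) or power for growth. Their only power figure concerns hearing.

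**Inputs from the documents.** 54 children, 27 per arm (SAP 5); ages 1 month up to the 4th birthday (SAP 4.3); four age bands by two birth-status groups, so 8 strata (SAP 4.1); growth visits on Days 1, 14 and 28 (SAP 4.5).

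**Assumed inputs.** Age uniform over 1-48 months; median weight rising from 4.3 to 16 kg; SD of Day 28 weight about 3.2 kg; SD of 28-day change 0.2, 0.3 or 0.4 kg; randomisation blocks of 2, 4 or 8; two-sided 5% level. Average 28-day gain = (16 − 4.3)/47 × 28/30.4 = 0.229 kg.

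**Step 1: signal against noise, suppose treated children gain nothing (0.23 kg deficit).**

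- Recorded weight: standard error = 3.2 × √(2/27) = 0.871 kg, so the signal is 0.23/0.871 = 0.26 standard errors.
- Change from Day 1, SD 0.3 kg: standard error = 0.3 × √(2/27) = 0.082 kg, so the signal is 0.23/0.082 = 2.8 standard errors.
- Wilcoxon by hand: 0.264 × √(3/π) = 0.258. Power = P(Z > 1.96 − 0.258) + P(Z < −1.96 − 0.258) = 0.044 + 0.013 = 5.8%, barely above 5%.

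**Step 2: simulated power (1,200-3,000 trials per setting).** Adjusted change means change from Day 1 adjusted for Day 1 weight and age stratum, under stratified allocation.

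| Deficit by Day 28 | Wilcoxon, stratified blocks | Wilcoxon, no stratification | Adjusted change, SD 0.2 / 0.3 / 0.4 kg |
|---|---|---|---|
| 0.115 kg (gain halved) | 0.1-0.6% | 4.7-5.4% | 43-46 / 25-27 / 16-18% |
| 0.23 kg (no gain) | 0.03-0.7% | 5.1-5.7% | 95-97 / 74-75 / 50-52% |
| 0.3 kg (more than the average gain) | 0.2-0.4% | 5.7-6.2% | 99.7-99.9 / 92 / 74% |

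The false-positive rate of the adjusted change was 4.4-5.3%. For length (assumed gain 0.92 cm, SD 12.4 cm), a 0.5 cm deficit gave 0.0% for the Wilcoxon, against 77, 58 and 42% for adjusted change at SDs of change of 0.6, 0.8 and 1.0 cm.

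**Step 3: against the model the SAP already lists.** A second simulation (2,000 trials per setting, weight SD about 3.1 kg, no stratified allocation) compared three analyses. Here the adjustment was for Day 1 weight and log age, and visit was a category, so the therapy-by-time test has 2 degrees of freedom.

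| Deficit | SD of change | Wilcoxon | Listed model, 2-df test | Adjusted change |
|---|---|---|---|---|
| 0.2 kg | 0.22 kg | 5% | 91% | 98% |
| 0.2 kg | 0.32 kg | 5% | 62% | 66% |
| 0.3 kg | 0.22 kg | 7% | >99% | >99% |
| 0.3 kg | 0.32 kg | 6% | 92% | 94% |

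At 0.23 kg and SD 0.3 kg, the same comparison gave 75% against 76%. The gain over the whole SAP is therefore about 0-7 points.

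**Step 4: the single contrast.** With no treatment effect, the 2-df test rejected 5-6% of the time, but the Day 28-minus-Day 1 contrast from the random-intercept model rejected about 8-10%. The reason can be shown by hand. Let s² be the variance of true 28-day gain between children and τ² the visit-to-visit variance. The true variance of change is s² + 2τ², while the random-intercept model uses about s²/2 + 2τ². At SD of change 0.217 kg and τ = 0.1 kg, the true variance is 0.0471, s² = 0.0471 − 0.0200 = 0.0271, and the model uses 0.0135 + 0.0200 = 0.0335. The standard error is too small by √(0.0471/0.0335) = 1.185, and the real error rate is 2 × P(Z > 1.96/1.185) = 9.8%.

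**The case against.** The strongest reply is that the SAP already contains the right analysis. Tables 18b and 18c are the listed weight and length tables, and their therapy-by-time term compares growth within children. In that block of the list, the Wilcoxon appears only for dose (Table 18a). The number and endpoint columns slip by a row there, but the formal-analysis column follows the titles; otherwise length would be assigned Fisher's exact test. This reply stands. A reader might infer that the SAP has no sensitive growth test, or that the full gap in Step 2 would be lost. The documents support neither, because the relevant comparator is the listed model and the gap to it is 0-7 points.

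The reply does not settle which result leads. Section 9.6 states a different test on the same data and promises comparison at each time point. Section 9.5 uses the same type of mixed model for laboratory values, also to compare arms at each time point rather than to compare change. Reading 9.6 alongside 9.5 would therefore still give by-visit comparisons.

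Two further replies also stand. Every growth figure is assumed, and the near-zero power depends on assumed small blocks. And nothing turns on the result: growth is not a primary, secondary or tertiary endpoint, the halting rule concerns neutropenia, and weight loss is graded separately against the child's own baseline (Grade 2 is "5 – 9% loss in body weight from baseline" in Protocol Appendix B). That grading does not, however, capture slower gain without loss.

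**Conclusion.** The point holds as a minor one about what Section 9.6 states. The by-visit Wilcoxon cannot detect even complete loss of 28-day growth under the assumed SDs: power is about 5-6% without stratified allocation and below 1% with small stratified blocks. The SAP as a whole is much less exposed, because the overall therapy-by-time test in Tables 18b/18c is sensitive. What remains is that 9.6 does not point to that model or name a change contrast, and that the obvious single contrast from a random-intercept-only model has a false-positive rate of about 8-10%.

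A reader might also infer that growth harm would be missed in a way that affects the trial's conduct. The documents do not support that, since no decision rule uses growth and the one growth signal they cite favours the drug. Nor would the fix make the trial informative about modest effects: in the Step 2 simulations, a halving of gain would be detected 16-46% of the time. All of this rests on assumed growth curves, SDs, age distribution and block sizes.

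**What to change.** In SAP 9.6, define the growth comparison as the change in weight and in length from Day 1 to Day 28, adjusted for the Day 1 value and age stratum, reported as a treatment difference with a 95% confidence interval. An acceptable alternative is to cite Tables 18b/18c and name their Day 28-minus-Day 1 therapy-by-time contrast, fitted with an unstructured covariance rather than a random intercept alone. Keep the by-visit Wilcoxon and the graphs as descriptive.

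Add that the trial cannot exclude modest slowing of growth. For an unadjusted difference in change with SD 0.3 kg, the half-width of the interval would be about 2.007 × 0.3 × √(2/27) = 0.16 kg, against an assumed average gain of 0.23 kg.

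The cost is one or two sentences. The three weights and lengths and the age stratum are already collected, and the mixed model is already planned.

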## **6.3. Modification of Study Intervention/Investigational Product for a Participant**

Bone marrow suppression secondary to CMV can mimic ganciclovir toxicity. Nevertheless, the dosage of valganciclovir will be reduced or interrupted if any of the following occur.

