### **6.3.1. Neutropenia**

If the ANC reproducibly (within one week) decreases to  $\leq 500$  cells/mm^3, study drug will be held until the ANC recovers to  $> 750$  cells/mm^3, and then administration of the drug will resume at the normal dose. If the ANC again reproducibly (within one week) decreases to  $\leq 750$  cells/mm^3, the study drug dosage will be reduced by 50% and maintained there as long as the ANC remains  $> 500$  cells/mm^3. If the ANC reproducibly (within one week) decreases to  $\leq 500$  cells/mm^3 on the 50% dosage, then the study medication will be discontinued. In cases of drug interruption, treatment will not be prolonged beyond the originally scheduled 6 week treatment timeframe.

Administration of granulocyte colony stimulating factor (GCSF) is allowed. All administered GCSF doses will be recorded on the concomitant medication sheet. The decision to utilize GCSF is left to the medical discretion of the participating investigator. The parameters for dose adjustment stated above, based upon ANC, will remain in effect even if the patient is receiving GCSF.

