### **7.2. Randomization (Window Day -30 to Day 1) and Baseline (Window: Day -3 to Day 1)**

- Document congenital CMV infection
- Obtain randomization authorization from UAB data center
- Baseline studies will be performed following randomization of the subject on the trial
- Document baseline demographics, selected laboratory parameters, medical history, and baseline conditions (Study Day -30 to Study Day 1) (see Section 8.1.1)
  - Date of birth
  - Gender
  - Race
  - Ethnicity

- Birth weight
  - Length at birth, if available
  - Head circumference at birth, if available
  - Gestational age at birth
  - Petechiae at any time from birth through study randomization, if known
  - Thrombocytopenia at any time from birth through study randomization, if obtained
  - Hepatomegaly at any time from birth through study randomization, if noted
  - Splenomegaly at any time from birth through study randomization, if noted
  - CSF white blood cell count at any time from birth through study randomization, if obtained
  - CSF protein concentration at any time from birth through study randomization, if obtained
  - CSF CMV PCR at any time from birth through study randomization, if performed
  - Seizures at any time from birth through study randomization, if noted
  - Elevated transaminases at any time from birth through study randomization, if obtained
  - Elevated bilirubin at any time from birth through study randomization, if obtained
  - Neuroimaging abnormalities, if obtained
  - Medical history and baseline conditions prior to study randomization, by body system
  - Chorioretinitis
  - Intrauterine growth restriction
  - Urine CMV testing (e.g., viral culture, shell-vial culture, PCR) within 90 days prior to study enrollment, if obtained clinically
- Hematology safety labs (see Sections 6.3 and 8.2.1.1)
    - WBC with differential
    - Hemoglobin
    - Platelet count
  - Chemistry safety labs (see Sections 6.3 and 8.2.1.2)
    - ALT
    - Total Bilirubin
    - Creatinine
  - Weight and length (see Section 8.1.2)
  - Adverse event assessment (see Section 9)
  - Concurrent medications assessment (see Section 6.6.1)
  - Obtain a new hearing assessment or record results from clinically obtained hearing assessment (may be obtained any time from Study Day -90 to Study Day -1) (see Section 8.1.4)

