    - BSER or VRA (to assess neuro-otologic status) and OAEs (DPOAE or TEOAE) will be obtained. If the BSER and/or VRA is abnormal, then bone conduction will be obtained to distinguish between sensorineural hearing loss, conductive loss, or mixed loss. If the OAEs are abnormal, then acoustic immittance measures (tympanometry and acoustic

reflexes) will be obtained to better define the middle or inner ear abnormality (e.g., otitis media).

- Virology specimens for CMV viral load (see Section 8.2.2.1)
- Confirm that Study Day 1 safety labs allow for dosing of study medication (see Section 6.3); if so, begin study medication on Study Day 1
- Updated results of any etiological investigations for SNHL.

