#### **8.1.3. Adverse Event Assessment**

At each study visit from the receipt of first dose of study drug and continuing through four weeks following the final dose of study drug, the study subject will be assessed for any adverse events (see Section 9).

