|---|-----|---------------------------------|---|----------------------|----------------------|-----------------------------------|--|
| Table 11a: Changes over Time in Hematology Parameters | 11a | At least one dose of study drug | Hematology Parameters | Baseline-Month 6 | Therapy Group, Visit | N, Mean, SD, 10th pctl, 90th pctl | General linear mixed model with random intercept was fitted for each parameter. Each model contains therapy, time and therapy by time interaction. |
| Table 11b: Changes over Time in Chemistry Parameters | 11b | At least one dose of study drug | Chemistry Parameters | Baseline-Month 6 | Therapy Group, Visit | N, Mean, SD, 10th pctl, 90th pctl | General linear mixed model with random intercept was fitted for each parameter. Each model contains therapy, time and therapy by time interaction. |
| Table 12: Maximum Degree of Neutropenia (Lowest ANC) During Day 1-42 Period | 12 | At least one dose of study drug | ANC | Randomization-Day 42 | Therapy Group | n, % | NA |
| Table 13: Maximum Degree of Anemia (Lowest HGB) for 11-0069 Valganciclovir | 13 | At least one dose of study drug | HGB | Randomization-Day 70 | NA | n, % | NA |
| Table 14: Maximum Degree of Anemia (Lowest PLT) for 11-0069 Valganciclovir | 14 | At least one dose of study drug | PLT | Randomization-Day 70 | NA | n, % | NA |
| Table 15: Maximum Degree of ALT (Highest ALT) for 11-0069 Valganciclovir | 15 | At least one dose of study drug | ALT | Randomization-Day 70 | NA | n, % | NA |
| Table 16: Maximum Degree of Creatinine (Highest creatinine) for 11-0069 Valganciclovir | 16 | At least one dose of study drug | creatinine | Randomization-Day 70 | NA | n, % | NA |
| Table 17: Summary of Concomitant Medications by Treatment Group (Blinded Treatment Phase) | 17 | At least one dose of study drug | Treatment Group (Blinded Treatment Phase) | Baseline-Day 48 | Therapy Group, Visit | n, % | NA |
| Table 18a: Dose (mg/kg) of Valganciclovir or Placebo | 18a | At least one dose of study drug | Dose | Day 1, 14 28 | Therapy Group, Visit | N, Mean, SD, Median, Min, Max | Fisher's exact and Wilcoxon test |

| | | | | | | | |
|---|-----|---------------------------------|---------------------------------|----------------------|----------------------|-------------------------------|--|

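### SAP Table 12 counts on-treatment neutropenia by arm over a span that includes the pre-dose ANC, so a child low before the first dose is tabulated as an on-treatment case

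*SAP*

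**What the plan says.** The Table 12 row in the SAP 17 table list is titled "Maximum Degree of Neutropenia (Lowest ANC) During Day 1-42 Period". Its population, endpoint, span, grouping, statistics and formal-analysis cells read "At least one dose of study drug | ANC | Randomization-Day 42 | Therapy Group | n, % | NA". The table is thus a count of dosed children by lowest ANC, split by arm.

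The order of events comes from the protocol. The heading of section 7.2 sets the windows: "Randomization (Window Day -30 to Day 1) and Baseline (Window: Day -3 to Day 1"). The section then states: "Baseline studies will be performed following randomization of the subject on the trial". It lists white cells with differential among those studies, and before treatment starts the site must "Confirm that Study Day 1 safety labs allow for dosing of study medication". The visit schedule in SAP 4.5 puts this draw in the Study Day 1 column, with a window of Day -3 to Day 1. The later hematology draws are at Days 14, 28, 42 and 70.

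On low counts, protocol 6.3.1 says that once the ANC is reproducibly at or below 500/mm3, "study drug will be held until the ANC recovers to" above 750. Protocol 5.3 has no ANC exclusion. In Protocol Appendix B, grade 3 is 500-749/mm3 and grade 4 is below 500.

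**The concern.** A table of worst on-treatment grade should contain only values that the drug could have affected. If the pre-dose ANC is eligible to be the lowest value, a child can be classed on a sample taken before any drug was given.

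The protocol makes such cases plausible in this population: "Bone marrow suppression secondary to CMV can mimic ganciclovir toxicity". The start of the window also carries weight because protocol 9.4 presumes that neutropenia in the treatment period is drug-associated, and 9.6.2 names it as the only laboratory toxicity that earlier studies by this group tied statistically to treatment. Table 12 is the by-arm display of that toxicity. Adding cases that arise equally in both arms makes the arms look more alike than they are.

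**Working it through.** **Step 1. Is a pre-dose value inside the span?**

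- Literal reading of the span cell (randomization to Day 42): the baseline draw follows randomization and precedes the first dose, so it is inside.
- Reading by the title (Day 1 to 42): SAP 4.5 labels the same draw as the Study Day 1 visit, and a sample taken on Day 1 itself to clear dosing is still pre-dose. It is inside again.
- Neither SAP 9 nor SAP 17 has a rule that drops it or counts only worsening.

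Of the four scheduled draws that Table 12 can use (Days 1, 14, 28, 42), the first is pre-dose.

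**Step 2. Can it change a child's class?**

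Take a child with a pre-dose ANC of 600/mm3 and values above 1,300 at Days 14, 28 and 42.

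| Rule | Result |
|---|---|
| Protocol 5.3 | no ANC exclusion, so eligible |
| Protocol 6.3.1 | 600 is above 500, so dosing may start |
| SAP Table 12, lowest ANC | 600, grade 3 |
| Worst post-dose ANC | above 1,300, below grade 1 |
| Protocol 8.1.3 and 9.2.2 | not an adverse event |

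The last row follows because adverse events are assessed "from the receipt of first dose of study drug and continuing through four weeks following the final dose of study drug", and under 9.2.2 a condition already present at randomization counts only if its grade worsens. The child is in Table 12 and not in the adverse event tables.

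**Step 3. Direction and size.**

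There is no figure in the plan to reproduce, and no pre-dose neutropenia rate in either document. Let p be the proportion with grade 3-4 after dosing and b the proportion with it before dosing. b is equal in both arms in expectation, because drug has not started. If the two are independent:

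- counted rate = p + (1 - p) x b
- counted difference = (1 - b) x (p_active - p_placebo)

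For p, use the earlier phase III trial in protocol 2.1.2.1: 29/46 = 63% on IV ganciclovir and 9/43 = 21% untreated. For b, assume 2% to 10%.

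| b (assumed) | Active | Placebo | Difference |
|---|---|---|---|
| 0 | 63.0% | 21.0% | 42.0 points |
| 2% | 63.7% | 22.6% | 0.98 x 42.0 = 41.2 points |
| 5% | 64.8% | 24.9% | 0.95 x 42.0 = 39.9 points |
| 10% | 66.7% | 28.9% | 0.90 x 42.0 = 37.8 points |

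With 27 per arm and b = 10%, the extra children counted are 27 x 0.10 x 0.37 = 1.0 on active and 27 x 0.10 x 0.79 = 2.1 on placebo. The placebo arm gains more because more of its children have no post-dose event.

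If every child who is low before dosing is also low afterwards, the counted rates do not change and the difference stays at 42.0 points. Partial overlap falls in between.

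**The case against.** The best defence is that the randomization label is shorthand for the start of dosing. Elsewhere the list uses a baseline label where a pre-dose value is meant (Tables 11a, 11b, 17 and the viral-load tables). It uses the randomization label for the adverse event tables, whose data start only at Study Day 1. The list is also a rough index: Table 10a, an adverse event table, names serious events as its endpoint, and from Table 18b the endpoint column slips by a row. This stands as far as intent goes: the plan does not announce that pre-dose counts will be included. It does not settle the matter, because the Day 1 draw that clears dosing is pre-dose under the shorthand reading as well.

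It is also true that ANC has a separate comparison. SAP 9.5 and Table 11a fit therapy, time and their interaction and compare arms at each time point, which keeps the pre-dose visit apart. That analysis is sound on this point, and it limits what Table 12 can distort.

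A reader might go further and infer that SAP 9 leaves the neutropenia event open to choice after the data are seen, since it states no grade cut beside Fisher's test and Table 12 shows no formal analysis. The documents do not support that. Appendix B grades ANC, grade 3 or 4 is the only cut that either document uses for neutropenia incidence, and Table 12 shows the degree of neutropenia by arm. The empty test cell is a bookkeeping mismatch with SAP 9.

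**Conclusion.** The point holds as a minor defect in one safety table. As written, Table 12 can class a child as an on-treatment grade 3 case on a pre-dose sample, contrary to the worsening-only rule in protocol 9.2.2. In expectation this moves the comparison between arms toward no difference. In a single trial of this size, a chance imbalance in pre-dose cases could push it either way.

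The size is unknown. The 41.2 to 37.8 points against 42.0 rest on three assumptions: a pre-dose rate of 2% to 10%, independence of pre-dose and post-dose status, and rates borrowed from neonates given an intravenous drug. The shift is smaller with overlap, and negligible if few children start with a low ANC.

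Two stronger readings should not be drawn. One is that the trial loses power to detect neutropenia: Table 12 carries no test, so there is no planned power to lose. The other is a large fall in a risk ratio, obtained by pairing the 38% seen in the oral valganciclovir study with a low placebo rate. Every child in that study was treated, so the documents supply no such control rate, and the SAP plans no risk ratio. The primary endpoint and the per-visit ANC model are not affected. The Day 42 end of the span is a reasonable choice.

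**What to change.** In SAP 17:

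1. Set the Table 12 span to run from after the first dose through the Day 42 visit, and change the title to match. Replacing randomization with Day 1 is not enough, because the Day 1 sample is pre-dose.
2. Lay the table out as pre-dose grade against worst post-dose grade, by therapy group, so that baseline neutropenia stays visible and is not mistaken for a treatment effect.
3. Use post-dose values in Tables 13-16 (hemoglobin, platelets, ALT, creatinine), whose spans also start at randomization.

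The cost is a few cells in the table list and one cross-tabulation. It needs no new data, visit or blood draw.
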